15.1.4 SENSITIVITY ANALYSIS OF PRIMARY EFFICACY VARIABLE

A sensitivity analysis will be conducted on the primary endpoint using the PP population.

If the percentage of missing data for the primary endpoint is greater than 10% (data from > 10% patients is not recorded exactly at 4 hours (+/- 5 minutes), an additional complete case sensitivity analysis will be conducted, using only the observed 4-hour (+/- 5 minutes) data.

15.2. SECONDARY EFFICACY

15.2.1 SECONDARY EFFICACY VARIABLES

The secondary endpoints are:

Percentage of time during the 4 hour post dosing period with pH below pH 5

Number of occasions during the 4 hour post dosing period when pH falls below pH 4

Number of occasions during the 4 hour post dosing period when pH falls below pH 5

Document: Reckitt Benckiser GA1202 Statistical Analysis Plan

Author: [REDACTED]

Version Number:

Final 5.1

Version Date:

[25Feb2014]

Template No: CS_TP_BS016 – Revision 3

Reference: CS_WI_BS005

Effective Date: 01May2012

Page 17 of 29

Number of reflux episodes during the 4 hour post dosing period with pH below pH 4 for at least 5 minutes

Percentage of time during the first hour post dosing with pH below pH 4

Percentage of time during the first hour post dosing with pH below pH 5

Number of occasions during the first hour post dosing when pH falls below pH 4

Number of occasions during the first hour post dosing when pH falls below pH 5

The longest reflux time during the 4 hour post dosing period (i.e. the longest period with pH below pH 4)

The DeMeester scores during the 4 hour post dosing period.

The secondary efficacy analyses will be performed for the ITT population.

15.2.2 MISSING DATA METHODS FOR SECONDARY EFFICACY VARIABLES

Missing data for the percentage of time during the 4 hour post dosing period with pH below pH 5 due to early termination of recording will be derived in the same way as for the primary efficacy variable.

For the following secondary efficacy variables:

- Number of occasions during the 4 hour post dosing period when pH falls below pH 4
- Number of occasions during the 4 hour post dosing period when pH falls below pH 5
- Number of reflux episodes during the 4 hour post dosing period with pH below pH 4 for at least 5 minutes

If less than 2 hours post-dosing monitoring result for these variables is available, for whatever reason, the derived variable will be considered missing. If 2 or more hours post-dosing pH data is available then the variable will be multiplied by 4 / (hours of post-dosing pH data available). Any data recorded more than 4 hours post-dosing will be ignored when deriving these parameters.

The table below shows the implementation of adjustment rules (take number of occasions as an example) under different monitoring duration scenarios.

Monitoring Duration(End of pH monitoring – taking treatment)	Number of occasions with pH<4 during the monitoring period (data directly from database)	Adjustment factor	Adjusted occasion with pH<4 over 4 hours
240 mins (4 hours)	2	1	2
230 mins (<4 hours)	2	240/230	2*240/230=2.09
90 mins (<2 hours)	1	NA	missing

Missing data for other secondary endpoints due to early termination of recording will not be derived.

Document: Reckitt Benckiser GA1202 Statistical Analysis Plan

Author:

Version Number:

Final 5.1

[25Feb2014]

Template No: CS_TP_BS016 – Revision 3

Effective Date: 01May2012

Reference: CS_WI_BS005

Page 18 of 29

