14.4 Efficacy Analyses

Results will be summarised by treatment for each dosing visit and overall (Compound Sodium Alginate Double Action Chewable Tablets, matching placebo tablets) using n, mean, standard deviation, median, minimum and maximum values.

If less than 2 hours post-dosing monitoring data is available, for whatever reason, (or less than 1 hour post-dosing data within the first hour for parameters based on the first hour post-dosing) the derived parameters will be considered missing. If 2 or more hours post-dosing monitoring data is available, the parameters will be derived using the data available, and will be adjusted, where necessary, by multiplying by the factor (4 hours / time with data available). Any data recorded more than 4 hours post-dosing will be ignored when deriving these parameters.

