15.1.2. MISSING DATA METHODS FOR PRIMARY EFFICACY VARIABLE

If less than 2 hours post-dosing monitoring result for this variable is available, for whatever reason, the derived variable will be considered missing. If 2 or more hours post-dosing monitoring data is available, the parameter will be derived by multiplying by the factor (4 hours / time with data available). Any data recorded more than 4 hours post-dosing will be ignored when deriving these parameter.

The table below shows the implementation of adjustment rules under different monitoring duration scenarios.

Monitoring Duration(End of pH monitoring – taking treatment)	Percentage of time with pH<4 during the monitoring period (data directly from database)	Number of hours with pH<4 during the monitoring period	Adjustment factor	Adjusted percentage with pH<4 over 4 hours
240 mins (4 hours)	80.0%	240 mins	1	80.0%
230 mins (<4 hours)	80.0%	230*80% mins	240/230	230*80%*240/230/240=80.0%
90 mins (<2 hours)	20.0%	90*20% mins	NA	missing

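### The SAP's adjustment tables run on clock time while its own text and the protocol run on time with pH data, so a session with signal loss inside the 4 hours is handled in two different ways

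*SAP*

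**What the plan says.** Protocol 14.4 (repeated in synopsis 3.11) sets two rules for the 4-hour parameters. They are missing in the case "If less than 2 hours post-dosing monitoring data is available, for whatever reason". Otherwise they are derived from what was recorded and adjusted where needed by "multiplying by the factor (4 hours / time with data available"). Both rules turn on how much data there is.

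The SAP prose keeps this. For the primary endpoint, SAP 15.1.2 states that "the parameter will be derived by multiplying by the factor (4 hours / time with data available"). For the three 4-hour counts (occasions below pH 4, occasions below pH 5, and episodes below pH 4 lasting at least 5 minutes), SAP 15.2.2 states: "If less than 2 hours post-dosing monitoring result for these variables is available, for whatever reason, the derived variable will be considered missing". With 2 hours or more, "then the variable will be multiplied by 4 / (hours of post-dosing pH data available").

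Each section then gives a worked table. The one in 15.2.2 is introduced so: "The table below shows the implementation of adjustment rules (take number of occasions as an example) under different monitoring duration scenarios". In both sections the first column is headed "Monitoring Duration(End of pH monitoring – taking treatment"), and the rows are 240, 230 and 90 minutes.

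SAP 15.1.4 and 15.2.4 add a complete-case analysis when more than 10% of patients lack data recorded at 4 hours, within 5 minutes.

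**The concern.** End of monitoring minus dosing is elapsed time. It equals time with data only if the signal is unbroken between those two points. If a probe loses contact and recovers, the elapsed time stays at 240 minutes while the usable data shrink. The prose then asks for rescaling or for a missing value, and the table asks for neither.

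A programmer could reasonably follow the table, because it is presented as the implementation. The inputs that the SAP names also fit it: SAP 14 and 14.1 list and derive clock times, and the tables take counts and percentages straight from the database. The SAP points to no item that gives minutes of valid signal.

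At stake are the values of three secondary endpoints and the inclusion of sessions with little data in any 4-hour analysis. The complete-case set is also affected, because its test, read as recording having run to 4 hours, can admit a session with a gap in the middle. The study is open-label, so the choice between the two inputs should be settled before sessions are viewed by treatment.

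**Working it through.** **Inputs.** The scaling rule and 2-hour cut-off come from Protocol 14.4 and SAP 15.1.2 and 15.2.2. The worked rows come from the two SAP tables. All gap lengths below are assumptions, since the documents give none.

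**Formulas.** Let T be the duration in minutes.
- Missing if T < 120.
- Otherwise adjusted count = count × 240/T.
- Adjusted percentage = (T × p × 240/T)/240.

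The table takes T as clock time, and the text takes T as minutes with data.

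**The plan's own figures.** At 230 minutes with 2 occasions, 2 × 240/230 = 2.087, shown as 2.09. At 230 minutes with 80%, 230 × 0.80 × 240/230/240 = 80.0%. Both reproduce. The rows are one full session and two that stop early. With an unbroken signal, clock time and data time coincide in all three, so the tables never show the case where the definitions differ.

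**Session ending at 240 minutes with an internal gap, 2 occasions counted:**

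| Assumed gap (min) | Data (min) | Table factor and count | Text factor and count | Table below text |
|---|---|---|---|---|
| 10 | 230 | 1; 2.00 | 1.043; 2.09 | 4.2% |
| 30 | 210 | 1; 2.00 | 1.143; 2.29 | 12.5% |
| 60 | 180 | 1; 2.00 | 1.333; 2.67 | 25% |
| 90 | 150 | 1; 2.00 | 1.6; 3.20 | 37.5% |
| 120 | 120 | 1; 2.00 | 2; 4.00 | 50% |
| 130 | 110 | 1; 2.00 | missing (110 < 120) | – |

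The shortfall is 1 − data/240; for a 60-minute gap, 1 − 180/240 = 25%.

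**Session that stops early and also has a gap.**
- Clock 230, gap 60, data 170: the table gives 2 × 240/230 = 2.09 and the text gives 2 × 240/170 = 2.82. The table rescales, but too little.
- Clock 150, gap 40, data 110: the table gives 2 × 240/150 = 3.20, and the text sets the value to missing.

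**Percentage endpoints.** T cancels in the formula, so 20% stays 20% under either input if the recorded percentage is a share of recorded time. Only the 2-hour cut-off can then change the result. In a session that runs to 240 minutes, this needs more than 120 minutes lost. The SAP does not state the denominator. If the software divided by clock time (an assumption), 20% of 180 recorded minutes would be entered as 20% × 180/240 = 15%, and a factor of 1 would not correct it.

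**The case against.** The best defence is that the right rule is already there. It stands in the prose directly above each table, and the tables only illustrate sessions of different length. No row or sentence assigns a factor of 1 to a session with a gap. This stands: the fault is a conflict between text and table. It does not remove the conflict, because the table is offered as the way the rule is carried out and its input differs from the rule's.

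Five stronger readings are tempting, and the documents do not support them.
- *That SAP 15.2.2 considers only early termination of recording.* That wording applies to the percentage below pH 5 and to the remaining secondary endpoints. The paragraph on the three counts covers loss of data from any cause.
- *That the counts would truly be 25% too low.* The 25% is measured against the rescaled value, which assumes the same reflux rate during the gap. If no episode fell in the gap, the raw count is right and rescaling inflates it.
- *That the primary result is materially distorted.* The factor cancels, and the clock-denominator case is only a possibility. Patients are supervised in clinic with the electrode taped in place (Protocol 11.3.2.1), so losing more than 2 hours unnoticed would be unusual.
- *That gapped sessions would count as complete throughout.* The PP criteria require complete 4-hour data at both visits, which can fairly be read to exclude them, and set membership is agreed before database lock. The SAP does not define complete, however, and the complete-case test looks only at the 4-hour point.
- *That valid signal time is not collected.* The primary variable comes from a CRF results page that is not among the documents, and non-substantial amendment 1 refers to separate pH monitoring guidelines, also not included. Either may cover it.

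Nothing suggests that gaps would differ by treatment, so no direction of bias can be claimed. The counts are also supportive endpoints only.

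**Conclusion.** The SAP is inconsistent about the input to its adjustment rule, and its tables, taken literally, depart from the protocol whenever signal is lost inside a session. For the three 4-hour counts, a full-length session falls short of the protocol's value by 12.5% to 50% for assumed gaps of 30 to 120 minutes, with 25% at 60 minutes. For all five endpoints under the rule (the three counts and the two 4-hour percentages), a session with under 2 hours of data may be kept when the protocol sets it to missing. For the primary endpoint that is the only effect, provided the recorded percentage is a share of recorded time. The overall effect on the trial cannot be sized, because gap frequency and length are not given. It is a modest point, worth correcting because a stated rule and its stated implementation disagree and the correction costs little.

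**What to change.** In the tables of SAP 15.1.2 and 15.2.2, redefine the first column as minutes of valid pH data from 0 to 240 minutes post-dose. Add one row with an internal gap, for example recording ended at 240 minutes, 60 minutes lost, 180 minutes of data, factor 240/180 = 1.33. State the denominator of the recorded percentage. Use the same figure for the 2-hour rule, the scaling factor, the completeness condition of the PP population, and the trigger and set for the complete-case analyses in 15.1.4 and 15.2.4.

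While the 15.1.2 table is open, correct its 240-minute row: it lists 240 minutes below pH 4 at 80%, whereas 80% of 240 is 192.

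The cost is one data item per session from the logger file, if it is not already held, and edits to two tables and the related definitions. The downside is that a few more sessions may be classed as short or missing.

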15.2.3 ANALYSES OF SECONDARY EFFICACY VARIABLES

The analysis methods for all secondary endpoints will be identically to those described for the primary endpoint in 15.1.3.

15.2.4 SENSITIVITY ANALYSES OF SECONDARY EFFICACY VARIABLES

Sensitivity analyses will be conducted on the secondary endpoints using the PP population.

If the percentage of missing data for the secondary variables listed in section 15.2.2 is greater than 10% (data from > 10% patients is not recorded exactly at 4 hours +/- 5 minutes), an additional complete case sensitivity analysis will be conducted, using only the observed 4-hour (+/- 5 minutes) data.

16 SAFETY OUTCOMES

All outputs for safety outcomes will be based on the Safety Population.

16.2 ADVERSE EVENTS

Adverse Events (AEs) will be coded using MedDRA version 16.0. For an individual patient, only adverse events commencing after first dose of IMP and no later than last dose of IMP+1day will be included in the AE and serious adverse event (SAE) summaries. AEs that began prior to the first dose of IMP or more than one day after the final dose of IMP will not be included in the analysis. Where an AE start date is partially or completely missing, and it is unclear using partial dates as to whether the AE is treatment-emergent, it will be assumed that it is.

16.2.1 ADVERSE EVENTS

An overall AE summary presenting the number and percentage of patients within the following categories by treatment sequence group and total will be provided.

- Total number of AEs (each patient might be counted more than once within this item)
- Patients with AEs
- Patients with SAEs
- Patients with AEs with a relationship to IMP as “Possible”, “Probable” and “Certain”
- Patients with severe AEs
- Patients with AEs leading to IMP dose change
- Patient with AEs leading to IMP permanently discontinued

In addition, an analysis using McNemar's test to compare the AE incidence during the 4-hour post dosing period between treatments will be presented for the following categories:

- Total number of AEs (note that for this item only the total numbers will be presented, no comparison on McNemar's test will be performed)
- Patients with AEs
- Patients with SAEs
- Patients with AEs with a relationship to IMP as “Possible”, “Probable” and “Certain”
- Patients with severe AEs

In addition, following tables will be reported by treatment sequence group:

- AEs, by SOC, PT and severity
- Related AEs, by SOC, PT and severity

The tables above will be repeated for adverse events occur during the 4 hour post dosing period by treatment.

Individual listings on adverse events, related adverse events (see definition in section 16.1.1.2), serious adverse events, adverse events leading to dose change/study discontinuation and death will be reported.

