3.6 Sample Size

The number of patients enrolled for this study has been derived from experience of previous pH monitoring studies conducted with other Gaviscon® formulations. It is anticipated that 36 evaluable patients will be required to complete the study. In order to achieve this, 44 patients will be enrolled in this study.

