14.1 Sample Size Justification

No statistical justification for the sample size in this study was performed because the variance of the response is not known for Compound Sodium Alginate Double Action Chewable Tablets.

The number of patients enrolled for this study has been derived from experience of previous pH monitoring studies conducted with other Gaviscon® formulations.. It is anticipated that 36

evaluable patients will be required to complete the study. In order to achieve this, 44 patients will be enrolled in this study.

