14.5.1 Adverse Events

All AEs will be coded using the most up-to-date version of MedDRA. For an individual patient, AEs that began prior to the first dose of IMP or more than one day after the final dose of IMP will not be included in the analysis.

The incidence of AEs (number and percent of patients reporting each type of AE at least once during the study) will be summarised for all AEs, by investigator attribution of relationship to IMP and by severity. The incidence of AEs will be compared among (between) treatment groups using McNemar's Test for all AEs, for those AEs classified by the Investigator as possibly, probably or certainly related to IMP and for severe AEs.

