6.4. STATISTICAL TESTS

The default significant level will be (5%); confidence intervals (CIs) will be 95% and all tests will be two-sided, unless otherwise specified in the description of the analyses.

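### The active-versus-placebo AE comparison rests on McNemar's test with no paired risk difference or confidence interval specified; with 36 to 44 pairs a non-significant result is weak evidence, and close to uninformative for rare SAEs and severe AEs

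*SAP*

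**What the plan says.** Under SAP 16.2.1, a McNemar analysis "to compare the AE incidence during the 4-hour post dosing period between treatments will be presented for the following categories". The four patient-level categories are any AE, SAEs, AEs judged related, and severe AEs. The total number of AEs is shown without a test. The list of tables assigns this to Table 14.3.1.2.

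Protocol 14.5.1 is close but not identical: "The incidence of AEs will be compared among (between) treatment groups using McNemar's Test for all AEs", then for related and severe AEs. It does not name SAEs and does not limit the comparison to the 4-hour window.

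The descriptive output is wider. "An overall AE summary presenting the number and percentage of patients within the following categories by treatment sequence group and total will be provided". The tables by SOC, PT and severity are also given by treatment for the dosing window: "The tables above will be repeated for adverse events occur during the 4 hour post dosing period by treatment".

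SAP 6.4 sets a general convention: "The default significant level will be (5%); confidence intervals (CIs) will be 95% and all tests will be two-sided". No interval or effect measure is attached to the AE comparison. The laboratory, vital-sign and physical-examination tests in SAP 16.4, 16.6 and 16.7 compare with baseline within sequence and overall, so McNemar's test is the only between-treatment safety inference.

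**The concern.** McNemar's test uses only patients who have the event on one treatment and not on the other. With few events and few patients, the p-value mostly reflects how little information there is. It does not show how large an excess on active the data still allow.

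The primary efficacy endpoint is handled differently. SAP 15.1.3 asks for least-squares means with 95% CI, and its code requests the treatment difference with confidence limits. The AE comparison gets a test alone. A reader of the study report would see a non-significant comparison without seeing which excesses had not been excluded.

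The test version is also open, and at these counts the version can change the result.

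**Working it through.** **Inputs from the documents.** Two-sided 5% level (SAP 6.4). Pairs: "It is anticipated that 36 evaluable patients will be required to complete the study" (protocol 3.6), with 44 enrolled. The figure 44 is an upper bound that assumes every enrolled patient is dosed at both visits. The plan states no power or precision for safety, so there is no figure to reproduce.

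**Assumptions, because the documents give none.** AE risks on active (pa) and placebo (pp) in the 4-hour window, the excess that would matter, and the within-patient correlation.

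**Step 1: smallest count that can reach 5%.** Let b be patients with the event on active only and c on placebo only. The asymptotic statistic is (b − c)²/(b + c) on 1 df. The exact p-value is twice the Binomial(b + c, ½) tail. With c = 0:

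| b | asymptotic p | exact p |
|---|---|---|
| 3 | 0.083 | 0.250 |
| 4 | 0.046 | 0.125 |
| 5 | 0.025 | 0.0625 |
| 6 | 0.014 | 0.031 |

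So 4 (asymptotic) or 6 (exact) is the minimum, with none in the other direction. At b = 5, c = 0 the two versions disagree. With b = c = 0 the asymptotic statistic is undefined.

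**Step 2: how often a true excess is missed.** Under independence p10 = pa(1 − pp) and p01 = pp(1 − pa). The number of discordant pairs is Binomial(n, p10 + p01). Given that number, active-only events are binomial with probability p10/(p10 + p01). Exact summation, counting rejections in the harm direction:

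| Active vs placebo | n = 36, asymptotic / exact | n = 44, asymptotic / exact |
|---|---|---|
| 2% vs 0% | 99.4% / >99.9% | 98.9% / >99.9% |
| 5% vs 0% | 90% / 99% | 82% / 98% |
| 10% vs 2% | 73% / 92% | 66% / 85% |
| 15% vs 5% | 73% / 85% | 68% / 79% |
| 20% vs 5% | 53% / 66% | 44% / 55% |
| 30% vs 5% | 18% / 26% | 10% / 16% |

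The first row can be checked by hand. All discordant pairs are active-only, so detection is P(X ≥ 4) or P(X ≥ 6) with X ~ Binomial(n, 0.02). P(X ≥ 4) is 0.6% at n = 36 and 1.1% at n = 44.

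**Step 3: sensitivity to the assumptions.** With placebo rates of 2–10% and correlation 0–0.3, power for a 5-point excess is 1–18%. For a 10-point excess it is 13–27% (exact) or 19–60% (asymptotic). At correlation 0, 50% power needs an excess of about 11–22 points and 80% power about 18–31 points.

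**Step 4: what an interval would add.** Tango score 95% upper limits for active minus placebo:

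| Discordant pairs (active only, placebo only) | n = 36 | n = 44 | p asymptotic / exact |
|---|---|---|---|
| 0, 0 | 9.6 points | 8.0 points | undefined / 1 |
| 2, 0 | 18.1 | 15.1 | 0.157 / 0.500 |
| 4, 1 | 23.2 | 19.4 | 0.180 / 0.375 |

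With no discordant pairs the limit is z²/(n + z²): 3.84/39.84 = 9.6% and 3.84/47.84 = 8.0%. With no events at all on a treatment, the exact one-sided 95% upper limit for its rate is 1 − 0.05^(1/n): 8.0% at n = 36 and 6.6% at n = 44.

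**The case against.** The strongest reply has five parts.

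- Per-treatment frequencies for the 4-hour window are planned and AEs are listed individually, so a crude difference can be worked out. This stands: the plan does not withhold all information on size. Marginal tables alone, however, do not give the discordant counts that a paired interval needs.
- The miss rates rest on assumed inputs. This stands too. Large excesses are usually found: at 30% versus 5% the miss rate is 10–26%. A reader might infer that a non-significant result carries no safety information in any row; the figures do not support that. For common AEs it argues against excesses of about 25–30 points or more.
- Neither document says that non-significance will be read as safety, and no safety margin or decision rule depends on the p-value. The stated objectives concern efficacy. This stands and limits the severity.
- SAP section 8 leaves table content to separate templates, which are not in the documents, so an interval might appear there. What can be said is that the SAP text specifies none.
- Protocol 14.1 says "No statistical justification for the sample size in this study was performed", but the reason given is the unknown variance of the response. That concerns efficacy and does not itself show that safety precision was neglected.

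After these concessions, a test of unnamed version remains the only between-treatment inference on AEs, without a specified estimate or interval.

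**Conclusion.** The point holds as a cheap improvement to a stated method. An excess of 5 points is missed at least 82% of the time in every scenario examined. At 15% versus 5% with independence, the miss rate is 68–85% depending on n and test version. For a category as rare as 2% versus 0% it is about 99% or more, so the SAE and severe-AE rows would be close to uninformative if such events are rare within 4 hours of one dose. These sizes depend on assumed rates and correlation; the 4-or-6 minimum does not.

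It would go too far to conclude that the test misses relevant harm whatever the rates, or that the sponsor plans to claim equal safety from p > 0.05. The first depends on rates and on a relevant excess that the documents do not define; the second is stated nowhere.

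**What to change.** In SAP 16.2.1 and Table 14.3.1.2:

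- Report, for each of the four categories, the active minus placebo paired risk difference with a 95% score interval, together with the discordant counts.
- Where events are zero or few, add an exact upper confidence limit for each treatment's own rate.
- Name the McNemar version where the test is kept. The asymptotic version agrees with the score interval about zero difference; the exact version may not, as at 5 versus 0.
- Omit the test for SAEs and severe AEs. Protocol 14.5.1 names severe AEs, so record that change in the SAP as a deviation, as the opening of protocol section 14 requires. The SAE row appears only in the SAP.
- State that a non-significant result will not be taken as evidence of comparable safety.

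The cost is SAP wording and a few extra table columns, with no new data. The downside is that the intervals will be wide and will look less reassuring than a non-significant p-value.
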